A. Body Weight – scales will be purchased and provided to the patient while participating in the study. All weights will be obtained on the same scale for each patient to assure consistency of measurements. Measurements will be performed in the preoperative holding area prior to surgery, the evening of surgery on the orthopaedic floor and every morning the patient is hospitalized using the same scale assigned to that patient. Body weight measurements will be repeated at home 48 hours' post-discharge and at one and two weeks either at home or in the clinic with the same scale as previously utilized. An additional measurement will be obtained at 3 weeks postoperatively if the patient's body weight at 2 weeks has changed more than +/- 2% from their preoperative value. Funding of the cost of the scales will come out of the CJR research funding.

B. Knee Range of Motion: This will be assessed preoperatively (at their clinic appointment), on POD #1 and 2 by the research staff if the patient has not been discharged, and at 1, 2, 3 and 4 weeks postoperatively by the outpatient physical therapy office. Patient standardized forms will be provided to the outpatient physical therapists to record all post-hospital measurements. Measurements will be done with a standard goniometer.

C. Leg Anthropometric (Girth) Measurements: girth measurements will be performed at 5 & 10 cm suprapatellar, midpatella, and 10 cm infrapatellar with the use of a standard tape measure. These measurements will be collected at their pre-operative visit by research staff, POD 1 and 2 by research staff, if the patient has not been discharged and post-discharge measurements will be performed by the outpatient physical therapist at the same intervals and recorded on the same outpatient data sheet as described in item B above.

D. Transfusion: Number of transfusions will be recorded and compared between both groups. Transfusion criteria will not deviate from our normal post-operative care protocol.

E. Wound Complications: the incidence of wound infection and wound drainage will be assessed and recorded. Compressive dressings will be changed daily until wound is dry. If wound is draining at hospital discharge, the patient will be provided with home dressing supplies and instructed on how to perform daily dressing changes. The patient will take a daily photo of the wound and removed dressing daily and email it to CJR until the wound is dry. This is standard protocol for our patients currently.

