F. Thromboembolic Disease: Screening will be based on clinical assessment of the participating medical team members, which is standard protocol with all of our patients. The incidence of thromboembolic events will be recorded. All patients in the study will use aspirin 81 mg twice daily for DVT prophylaxis.

G. Muscle Strength: quadriceps strength will be assessed on POD #1 and 2 by research staff (in the hospital) and repeated at 2 and 6 weeks postoperatively at their standard of care follow-ups in the office by research staff. The strength testing will be calculated using a handheld dynamometer which is standard testing for strength in many post-operative patients currently.

H. Functional Performance Assessment: Functional tests will be performed at their preoperative appointment and once again at their 2 and 6 weeks postoperatively and will include the timed up and go (TUG) and the 30 second sit-to-stand tests. The tests will be performed in the office by research staff. These are standard tests that are often performed in physical therapy clinics to assess patient progress.

I. Length of the Hospitalization & Readmission Incidence will be recorded for both groups.

J. Postoperative Pain Assessment: Pain will be assessed using a pain VAS scale daily while hospitalized, then three times per day for 4 weeks postoperatively. Patients will be given a log to record these measurements outside of the hospital setting.

K. Adverse Events: episodes such as symptomatic hypotension (light-headedness, syncope), emesis, the need the IV fluid boluses, and other hospital and post-discharge events will be recorded.

L. Blood Pressure: this will be recorded in the Preoperative Care Unit, PACU, upon arrival to the nursing unit, and every 8 hours thereafter while hospitalized. This is standard practice for all of our patients currently.

M. PONV (Post-operative Nausea and Vomiting) - PONV will be assessed throughout their hospital stay; vital signs are checked per hospital nursing protocol, patients will be asked about Nausea: None, Mild, Moderate or Severe.

N. Patient Reported Outcome – We will be collecting the Knee Society Score(KSS) Knee injury and Osteoarthritis Outcome Score (KOOS) and the VR-12 from the patients pre-operatively as well as at their 2 week and 6 week follow up appointments. These are validated patient reported outcome measures that are already collected as standard of care at Colorado Joint Replacement.

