Based on my reading of the fluid management protocol, the study evaluates the hypothesis that the euvoolemia regimen leads to better outcomes than the traditional regimen. The former corresponds to the treatment group and the latter to the control group for the analysis, and assuming that the two groups demonstrate similarities in terms of potential pre-treatment confounding variables, such as measures obtained from preoperative history and physical, a comparison of post-treatment outcomes seems appropriate (e.g., t-tests). Even under random assignment to treatment, checks can be performed to ensure effective equivalence of confounders across treatment and control groups, an essential step in the case of small samples. If the results of such checks reveal potential confounding, including control variables in the analysis may be appropriate (e.g., in a linear regression) or a matching design to generate treatment-control pairs can be used.

While I do not have any substantive training in this field, it seems that some of the outcomes listed in the Procedures: Primary Outcomes section of the protocol may be mediated by others. For example, the association between receiving the treatment and readmission or length of hospitalization may be mediated by some of the other outcomes listed. Are there any known or suspected mediators at this point, either from the list of outcomes or beyond?

Concerning statistical power, in the figure below I calculate power (y-axis) for a range of hypothesised values of estimated effect sizes (colored lines), sample sizes per treatment and control group (x-axis), and arbitrarily chosen levels of significance (α) across the panels. Regarding α , I start with 0.05 and then make an adjustment based on an arbitrary number of hypotheses to be evaluated (eight, in this demonstration). The solid horizontal line at 0.8 represents the commonly accepted power value. As an example from Figure 1(b), for a medium-high effect size of 0.6 (green line) and evaluating eight hypotheses, in order to achieve power of 0.8 would require approximately 65 participants in each of the treatment and control groups.

[figure not shown]

Figure 1: Power calculations for hypothetical effect sizes and sample sizes (per group) at given values of α . The left panel uses $\alpha = 0.05$ and the right panel employs a Bonferroni correction for multiple hypotheses. In this case, evaluating eight hypotheses with a desired α of 0.05 yields an adjusted α of 0.00625.

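### Section 9 does not say how repeated outcomes become one test each, so the number of tests, the significance level and the power are undefined

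*Combined protocol and SAP*

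**What the plan says.** Section 9 is the only analysis text. Section 11 merely refers back to the methods of evaluation, and the Section 14 attachments are logs and the envelope selection. On comparing the arms, Section 9 says "a comparison of post-treatment outcomes seems appropriate (e.g., t-tests". If balance checks suggest confounding, "including control variables in the analysis may be appropriate (e.g., in a linear regression", or matching, may be used. No time point, change score, summary measure or repeated-measures model appears for any outcome.

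The power paragraph takes "an arbitrary number of hypotheses to be evaluated (eight, in this demonstration" and the Figure 1 caption adds that "evaluating eight hypotheses with a desired α of 0.05 yields an adjusted α of 0.00625". The worked example is "for a medium-high effect size of 0.6 (green line) and evaluating eight hypotheses", giving 80% power with about 65 per group. Section 2 takes its recruitment target from this calculation.

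Section 2 (Primary Outcomes) lists 20 items, A to T. Ten have two or more postoperative values per patient: weight (A), ROM (B), girth (C), strength (G), function (H), pain (J), blood pressure (L), nausea and vomiting (M), patient-reported outcomes (N) and bioimpedance (Q). For girth, "girth measurements will be performed at 5 & 10 cm suprapatellar, midpatella, and 10 cm infrapatellar with the use of a standard tape measure". For pain, "Pain will be assessed using a pain VAS scale daily while hospitalized, then three times per day for 4 weeks postoperatively".

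**The concern.** A two-sample t-test takes one number per patient. Without a rule for producing that number, an analyst can test every visit, choose one visit or girth site, or form a summary, and can decide after seeing the data. Each route implies a different number of tests, and so a different significance level and power. Naming exactly eight primary outcomes would not close the gap, because each repeated outcome could still supply several tests.

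Two things are at stake. Testing value by value either inflates the false-positive rate or, if the correction is extended, costs much of the power on which 65 per group rests. Testing one visit keeps the test count down but discards measurements that the trial collects anyway.

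**Working it through.** **1. The plan's own figure.** Inputs from Section 9: effect 0.6 SD, α = 0.05/8 = 0.00625, power 0.80, about 65 per group. Two-sample t-test, 2 × 65 − 2 = 128 df, noncentrality 0.6 × √(65/2) = 3.42.
- One-sided: power 81.1% at 65; n for 80% is 64 per group.
- Two-sided: power 73.8% at 65; n for 80% is 73 per group.

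So 65 reproduces only as a one-sided test. Section 9 does not state sidedness, though its hypothesis is directional ("the study evaluates the hypothesis that the euvoolemia regimen leads to better outcomes than the traditional regimen"). Both versions are shown where they matter.

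**2. Scheduled postoperative values per patient (Section 2, Primary Outcomes).**

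| Item | Values | Count |
|---|---|---|
| A weight | evening of surgery, two inpatient mornings (assumed), 48 h after discharge, weeks 1 and 2 | 6 |
| B ROM | POD 1, POD 2, weeks 1–4 | 6 |
| C girth | 4 sites × 6 times | 24 |
| G strength | POD 1, POD 2, weeks 2 and 6 | 4 |
| H function | 2 tests × 2 visits | 4 |
| N patient-reported | 3 instruments × 2 visits, one score each | 6 |
| Q bioimpedance | POD 1, POD 2, weeks 2 and 6, one output each | 4 |

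The sum is 6 + 6 + 24 + 4 + 4 + 6 + 4 = 54. Pain adds 3 × 7 × 4 = 84, giving 138. (If the four weeks run from surgery and the stay is 1–2 days, an assumption, pain gives about 78–81.) Blood pressure and nausea are left out because their number depends on length of stay. These are scheduled maxima: several POD values exist only while the patient is in hospital, and Section 2 anticipates some POD 1 discharges.

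**3. Every value tested at 0.00625.** Chance of at least one false positive, if independent: 1 − (1 − 0.00625)^m.
- m = 8: 4.9%
- m = 54: 28.7%
- m = 138: 57.9%

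The values are correlated within patients. With an assumed correlation of 0.3 to 0.7 within each outcome and independence between outcomes, simulation gives roughly 27% down to 19% for 54 tests and 48% down to 28% for 138.

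**4. Every value tested, Bonferroni extended to 54.** α = 0.05/54 = 0.00093. Power at 65 per group and 0.6 SD falls from 73.8% to 51% two-sided, and from 81.1% to 60% one-sided.

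**5. One visit against the mean of several.** The documents give no within-patient correlation. Assume equal correlation ρ between visits and a constant 0.6 SD effect. The mean of k visits has variance factor v = (1 + (k − 1)ρ)/k and effective effect 0.6/√v. α = 0.00625, 65 per group.

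| | ρ = 0.5 | ρ = 0.7 | ρ = 0.9 |
|---|---|---|---|
| v, k = 6 | 0.583 | 0.750 | 0.917 |
| effective effect (SD) | 0.786 | 0.693 | 0.627 |
| power, two-sided (one visit 74%) | 95% | 88% | 78% |
| power, one-sided (one visit 81%) | 97% | 92% | 85% |
| k = 4 (weeks 1–4 only), two-sided | 94% | 86% | 78% |

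The effect detectable with 80% two-sided power falls from 0.64 SD to 0.49, 0.55 or 0.61 SD with six visits (0.637 × √v).

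**6. When averaging hurts.** If 0.6 SD is present at three of six visits and absent at the others, the mean effect is 0.3 SD. Two-sided power of the six-visit mean is then about 30%, 22% or 17% at ρ = 0.5, 0.7 or 0.9, against 74% for one affected visit.

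**The case against.** The strongest reply is that a t-test can handle a series perfectly well: take one summary per patient (mean, area under the curve or change) and test that. This is correct. It keeps one test per outcome, and the averaged figures in step 5 are exactly such a t-test. With complete, balanced data it matches a random-intercept model: in five simulated balanced data sets the two statistics agreed to within 0.0001. A reader might infer that only a longitudinal model recovers the lost power; that does not follow. What stands is that Section 9 prespecifies no such summary, and that POD values missing after discharge make the series incomplete by design, where a mixed model has a real advantage.

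Second, the t-test is only an example and the eight only a demonstration, so the plan breaks no commitment. That is also fair. Twenty listed outcomes exceed eight even at one test each (α = 0.05/20 = 0.0025; power at 65 is 63% two-sided, 71% one-sided), so the wider defect is that no set of hypotheses is fixed. But 65 per group was taken from this demonstration, and nothing firmer replaces it.

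Third, the power gain is conditional. It is small at ρ = 0.9 and can reverse (step 6). This stands, and it is a reason to choose the window in advance rather than to leave it open.

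**Conclusion.** The gap is real and should be closed before analysis: ten of twenty Primary Outcomes are series, and no rule turns any of them into one test. If every scheduled value is tested at 0.00625, the chance of a false positive is about 29% for 54 tests and 58% for 138 under independence, and lower with positive correlation. These are indications of scale, not estimates. Extending Bonferroni to 54 tests leaves 51% two-sided power. Testing one visit gives up about 5 to 22 percentage points of two-sided power (4 to 16 one-sided) relative to a six-visit mean, for ρ from 0.9 to 0.5. That assumes equal correlation between visits and a constant effect, neither of which the documents establish. The gain remains with only the four outpatient visits.

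A reader might go further and infer that most of the outcomes are series, or that repeated readings will be pooled as if independent. The documents support neither: the share is half, and Section 9 nowhere proposes pooling.

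**What to change.** Amend Section 9 to name one analysis and one test for each repeated outcome.

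- **Contrast:** the mean arm difference over a stated window, chosen outcome by outcome (for example through week 2 for girth and week 4 for ROM) and fixed before any outcome data are compared by arm.
- **Model:** a linear mixed model on all scheduled values with visit, treatment-by-visit, within-patient correlation and, where a baseline is collected, the baseline value. Section 2 schedules no baseline for strength or pain. The model uses patients whose POD values are missing after discharge, on the assumption that missingness is explained by the observed data. A t-test or ANCOVA on a per-patient summary is an acceptable equivalent when data are complete.
- **Reduction first:** average the four girth sites, and take weekly patient means for pain. Define a per-patient summary for the in-hospital blood pressure and nausea readings.
- **Visit-level differences:** report as secondary estimates with confidence intervals.
- **Multiplicity:** divide alpha by the number of outcomes actually tested, state sidedness, and restate power on that basis.

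The cost is SAP wording and modest extra analysis, with no added patients or measurements. The downside is the dilution in step 6: a poorly chosen window can miss an effect confined to a few visits, so the choice needs a stated rationale.

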***Traditional Intravenous Fluid versus Oral Fluid Administration in Primary
Total Knee Arthroplasty: A Randomized Trial***

Version 8.0 July 6th, 2017 - NCT03719378

Traditional Intravenous Fluid versus Oral Fluid Administration in Primary Total Knee Arthroplasty: A Randomized Trial

1. Purpose: Evidence-based guidelines on optimal perioperative fluid management have not been established in patients undergoing orthopaedic surgery. Typical intraoperative and post-operative fluid management has been arbitrary without evidence based guidelines established following total joint replacement. We have observed many patients post-operatively with side effects such as fluid overload leading to medical complications requiring either prolonged hospitalization or readmission. Additionally, this overload may lead to wound healing complications secondary to fluid shifts which may be devastating in this patient population. Recent randomized trials in major abdominal surgery suggest that large amounts of IV fluid may increase morbidity and hospital stay. Additionally, this increase fluid may be detrimental in patients with anastomosis leading to failure and/or complications in this patient population. We have defined to specific groups of interest to study in this patient population with regards to fluid management. The first group is the “traditional” IV fluid group where the anesthesiologist gives an unspecific amount of fluid intraoperatively and post-operatively the patient gets a set amount of fluid based on “protocol” on the orthopaedic floor (i.e. 75 cc/hour until good oral intake). This is the protocol utilized by most orthopaedic practices throughout the United States. The second group is defined as patients who are given a specific protocol preoperatively to optimize hydration, followed by limited fluids intraoperatively based on physiologic parameters. This study will investigate the effects of two regimens of intraoperative fluid management (“traditional” vs. “oral”) with physiologic and patient function as primary outcome measures after surgery.

2. Procedures:

- Patients meeting the inclusion criteria who are schedule for unilateral primary TKA will be identified.
- The patients will be approached regarding the study (in clinic by research staff) and if the patient is agreeable, informed consent will be obtained.

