- The patients will be randomized into the traditional vs. oral treatment groups (see below for details and protocol). The protocol for each group will be placed in sealed envelopes, 65 for each group, and picked randomly for each patient.
- The patients will attend their normal preoperative visits with the surgical team as well as their regularly scheduled preoperative clearance visit with the medical doctor (Surgery Welcome Center)
- Standard preoperative labs will be obtained (hematocrit, basic metabolic panel), at their preoperative appointment
- Additional preoperative labs will include urine specific gravity to monitor patient hydration which will be obtained the morning of surgery; this will be paid for by the CJR research fund.
- Standard laboratory values (hematocrit and basic metabolic panel) will be obtained postoperative day #1 and #2, if the patient has not been discharged.
- Urine output will be monitored on postoperative day #1 and #2 which is standard protocol
- Additional test will include urine specific gravity on postoperative day #1 and #2 as a marker of hydration as long as the patient is still in the hospital. If the patient is discharged postoperative day #1 we will collect this once in the morning, and once more before they are discharged. Payment of the cost of these laboratory evaluations will come from CJR research funds.
- Patients are encouraged to attend physical therapy 2-3 times a week for 6 weeks. Physical therapy log is attached with ROM and Girth measurement collected once a week for 4 weeks.
- Hematocrit, basic metabolic panel and urine specific gravity 2 weeks postoperatively at their routine follow-up visit will also be obtained. The cost of these laboratory tests will come from CJR research funding.
- Sixty-five patients in each group will be recruited for this study (see stats for power analysis). We will increase our number of enrollment to 75 in each group to account for patients that drop out and withdrawals from the study.

Traditional Fluid Protocol

- NPO Clears and Food after midnight.
- 2 Liters of lactated ringers administered by anesthesia intraoperatively.
- Postoperatively - 2 Liters of Crystalloid while in PACU and Inpatient Room for a Total of 4 Liters of Crystalloid within 24 hours.
 - Patient will receive 500 milliliters while in PACU and 1500 milliliters while in their Inpatient Room, for a total of 2 Liters.

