O. Pressors – We will be collection the total amount of any pressor drugs (e.g. Ephedrine and Phenylephrine) given intra-operatively and in PACU in both groups.

P. Oral Fluid Intake Log – The patients that are in the Oral group will have an additional page to keep track of their fluid intake prior to surgery.

Q. Bioimpedance machine - This will be used to track patients body composition before and after surgery. Research staff in the office will collect this information at the patient's pre-op visit, POD#1 and 2 as well as their 2 week and 6 week visit.

R. Body Temp – The patient's body temp will be recorded pre-operatively as well as in the recovery room.

S. Time from their last clear fluid drink to the start of anesthesia, this start up time will be recorded for both groups.

T. Patient perception/satisfaction with their fluid protocol.

Patient Withdrawal: subjects may withdraw from the study for any reason at any time. Should a subject decide to withdraw from the study, all data collected up to that point will be deleted and not used for statistical analysis. Withdrawal from the study will not affect the patient's treatment after their total knee arthroplasty.

3. Scientific Background of the Study – As stated in the “purpose” section –

Evidence-based guidelines on optimal perioperative fluid management have not been established in patients undergoing orthopaedic surgery. Recent randomized trials in major abdominal surgery suggest that large amounts of fluid may increase morbidity and hospital stay. This study will investigate the effects of two regimens of intraoperative fluid management (“traditional” vs. “oral”) with physiologic and patient function as primary outcome measures after surgery.

4. Specific Aims of the Study – This study will investigate the effects of two regimens of intraoperative fluid management (“traditional” vs. “oral”) with physiologic and patient function as primary outcome measures after surgery.

5. Description of risks and measures to minimize risks.

- All patients, regardless of their volume protocol (traditional vs. oral), will follow a traditional post-operative course which includes daily labs and monitoring physiologic status from both the orthopaedic and general medicine team.
- All patients will have traditional post-operative follow-up care which will not be varied.

Surgical Risks:

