10. Trial Design

- Please refer to the above sections regarding the discussion of the research study
- Patients will be identified based on the inclusion and exclusion criteria stated above. The patients will then be randomized into the “traditional” vs. oral arms of the study. Outside of the amount of preoperative, intraoperative and postoperative fluids given to the patients, there is no difference in the treatment or outcome measures between the 2 groups.

11. Statistical calculations- please refer to section 10, methods of evaluation

12. Confidentiality of the data.

- Data will be collected on a password protected excel spreadsheet that will be stored on a Centura password protected computer.
- All data collected will be de-identified.

Data sharing.

With whom will *identifiable* (contains any of the 18 identifiers) data be shared outside the immediate research team? For all that apply, explain confidentiality measures. Include data use agreements, if any.

Data will be shared with:		Name/Description/s
	No one	
	Coordinating Center	
	Statisticians	
x	Other researchers	[name]; [name]; [name]; [name], , [name], [name] (research coordinator), [name] (research data entry clerk), [name] (clinical research associate).
	Registries	
	Sponsor/s	
	External labs for additional testing	
	Journals	
	Publicly available dataset	
	Other	

Data security for storage and transmission. Include all that apply.

For electronic data stored on a desk top computer:

 Secure network	 Password access	 Data encryption	 Password protected file(s)
 Other comparable safeguard (describe):		Data will be de-identified	

For portable computing devices/external storage devices (e.g. laptop computer, PDA, CDs, memory sticks):

 Power-on password	 Data encryption
 Automatic log-off	 Password protected file(s)
 Other comparable safeguard (describe): Data will be de-identified	

For hardcopy data (including human biological specimens, CDs, tapes, etc.):

 Data de-identified by research team (stripped of the 18 identifiers)	 Locked suite or office

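### All 20 lettered items are primary outcomes, with no chosen endpoint, primary time point or multiplicity rule, and 65 per group comes from a demonstration with eight unnamed hypotheses

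*Combined protocol and SAP*

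**What the plan says.** The Primary Outcomes heading in section 2 covers items A to T. There is no secondary list and no ranking. Most items have a measurement schedule, but none has a designated time for the primary comparison. Sections 1, 3 and 4 narrow the aim only to two domains, "with physiologic and patient function as primary outcome measures after surgery".

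Section 9 is the only statistical text. It suggests t-tests as an example and plots power at significance levels it describes as arbitrary. It starts from 0.05 and then says it will "make an adjustment based on an arbitrary number of hypotheses to be evaluated (eight, in this demonstration". The Figure 1 caption adds that "evaluating eight hypotheses with a desired α of 0.05 yields an adjusted α of 0.00625". For a standardised effect of 0.6 the section concludes that "in order to achieve power of 0.8 would require approximately 65 participants in each of the treatment and control groups".

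Section 2 adopts that number: "Sixty-five patients in each group will be recruited for this study (see stats for power analysis". It then adds: "We will increase our number of enrollment to 75 in each group to account for patients that drop out". The Patient Withdrawal paragraph says that for a withdrawn patient "all data collected up to that point will be deleted and not used for statistical analysis". Section 11 adds no rule of its own: "Statistical calculations- please refer to section 10, methods of evaluation". Methods of Evaluation is in fact section 9.

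**The concern.** A confirmatory trial needs to say in advance which comparison decides it and at what error rate. Here 20 items share primary status, and ten of them (A, B, C, G, H, J, L, M, N and Q) are measured more than once after surgery. Some items hold several measures: girth has four sites, function has two tests, and patient-reported outcome has three instruments.

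The Bonferroni level belongs to a demonstration. It is not attached to named outcomes, and eight does not match the list. If no rule limits the tests, a difference on any item, site or visit can be reported as a primary finding, and the chance of at least one false finding is not held at 5%. The 80% power attached to 65 per group also depends on a number of tests, a sidedness and an effect size that the plan ties to no outcome.

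The list was not built as a family of tests either. Item P is kept only in the oral arm. Item S, the time since the last clear drink, is set largely by the two fasting instructions.

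**Working it through.** **Inputs from the documents.** 20 items (section 2); standardised effect 0.6, power 0.80, eight hypotheses, approximately 65 per group (section 9); 65 per group planned and 75 enrolled (section 2). Sidedness is not stated. Correlations and event rates are not given, so those below are assumptions.

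**1. The plan's own figure.** The corrected level is 0.05/8 = 0.00625, as stated. Two-sample t-test, noncentral t, effect 0.6, level 0.00625:
- One-sided: 80% power needs 64 per group; power at 65 is 81.1%.
- Two-sided: 80% power needs 73 per group; power at 65 is 73.8%.

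So 65 reproduces as a one-sided t-test and not as a two-sided one. Figure 1 is not shown, so its sidedness cannot be confirmed.

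**2. Number of testable items.** 20 less P (one arm only) and S (largely set by protocol) = 18. This counts headings with one test each; sites, instruments and visits would raise it.

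**3. Family-wise error, 18 two-sided tests.** If independent:
- at 0.05 each: 1 − 0.95^18 = 0.603
- at 0.00625 each: 1 − (1 − 0.00625)^18 = 0.107; the bound under any dependence is 18 × 0.00625 = 0.1125

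With equally correlated normal test statistics (assumed correlations):

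| Level per test | Independent | 0.3 | 0.5 | 0.7 |
|---|---|---|---|---|
| 0.05 | 60% | 51% | 40% | 28% |
| 0.00625 | 10.7% | 9.3% | 7.4% | 5.1% |

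Discrete tests on uncommon events lower these figures. Suppose four of the 18 were Fisher tests with an assumed 5% event rate in both arms. Their actual size is 0.0121 at 0.05 and 0.0012 at 0.00625. With independence:
- 1 − 0.95^14 × (1 − 0.0121)^4 = 0.535
- 1 − (1 − 0.00625)^14 × (1 − 0.0012)^4 = 0.088

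**4. Power at effect 0.6, level 0.05/k for k tests.**

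| Tests k | 65 per group, two-sided | 65, one-sided | 75, two-sided | 75, one-sided | n per group for 80% (two-sided / one-sided) |
|---|---|---|---|---|---|
| 8 | 73.8% | 81.1% | 81.4% | 87.2% | 73 / 64 |
| 18 | 64.4% | 72.4% | 73.5% | 80.3% | 84 / 75 |

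At 65 per group, two-sided power is 92.4% for one test, 81.1% for four and 78.8% for five, so four is the most that keeps 80%. One-sided, eight tests keep it (81.1%) and nine just miss (79.9%). The 75 columns assume that nobody is lost. For a single two-sided test at 0.05, the smallest effect with 80% power at 65 per group is 0.495.

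**5. Binary events.** The calculation for a mean says nothing about transfusion, wound infection, thromboembolism or readmission analysed as yes/no. With 65 per group and no events in one arm, Fisher's exact test gives p = 0.058 for 5 v 0 and p = 0.028 for 6 v 0. Six events against none are needed to reach 0.05.

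**The case against.** The best defence is that section 9 claims 80% power only for its example of eight hypotheses, and that the example is sound. The stated hypothesis is directional, and a one-sided t-test needs 64 per group. This stands: 65 is not a miscalculation, and no text proposes testing 18 items. But section 2 turns the example into the trial's sample size without naming the eight hypotheses, so the figure describes no analysis in the plan.

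Other points are fair and limit the size of the problem:
- The 60% figure needs independence and no correction. At 0.00625 each, the inflation runs only from 5.1% to 10.7%.
- No event rates are given, so calling some items rare is an assumption. Transfusions are recorded as a number, and the readmission item also holds length of stay, so the four-Fisher-test figures are only indicative.
- The count of 18 is a judgement. S is recorded in both arms, and early body weight or bioimpedance might also be seen as partly set by protocol.
- Several primary outcomes with a proper correction are legitimate. Naming the eight would also be a coherent repair.
- Enrolling 75 gives 81.4% two-sided for eight tests, but only if all 75 are analysed. The extra ten are there to cover losses, and withdrawn patients' data are deleted.

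None of this supplies a primary endpoint, a primary time point or a rule for the final analysis. The trial registry record and the attached logs were not available and could hold more detail.

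**Conclusion.** The concern holds and must be fixed. The plan has no designated confirmatory test, and nothing in it holds the family-wise error at 5%. For 18 items with one two-sided test each, that error is 28% to 60% at 0.05 per test and 5.1% to 10.7% at 0.00625, over assumed correlations from 0.7 down to independence. Uncommon binary outcomes would lower these figures; repeated visits, sites and instruments would raise them.

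The 80% power behind 65 per group is met at an effect of 0.6 for up to eight one-sided or four two-sided tests of continuous outcomes, but not for 18. The documents justify an effect of 0.6 for no outcome, so even these figures are conditional.

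**What to change.** Before any comparison by arm, name one primary outcome at one time point from the measures already collected. Test it two-sided at 0.05, adjusted for its preoperative value where one exists. The investigators should choose it; timed up and go at 2 or 6 weeks is one example. With 65 per group, an unadjusted t-test has 92% power at an effect of 0.6 and 80% at about 0.50. The effect size should be justified for the outcome chosen.

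Label the remaining items secondary, exploratory or safety. Treat P and S as adherence or process measures. Report uncommon events descriptively with confidence intervals.

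If several outcomes stay primary, list at most four continuous ones, each with one time point, under two-sided Holm. Power is then at least 81% each at 0.6, because the Bonferroni figure is a lower bound for Holm. If more are kept, including a named set of eight, replace the 80% with the power for that number of tests at 65 evaluable per group: 73.8% two-sided or 81.1% one-sided for eight, 64.4% or 72.4% for 18. State the sidedness in every case, and correct the cross-reference in section 11.

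The cost is protocol and SAP wording, with the registry entry made to match; no new measurement is needed. The downside is that confirmatory claims on the other outcomes are given up, and a late functional endpoint may miss early differences.
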